8.3.2. Exposure definitions

This is a binary comparison of COPD patients enrolled in the SLS and COPD patients in the CPRD. Hence the primary exposure of interest is whether a patient is enrolled in SLS (yes/no). A third grouping, COPD patients in Salford (who are not in SLS) will also be examined.

8.3.3. Confounders and effect modifiers

- Sex
- Age
- Socio-economic status (SES)
- Current/SOC COPD Medication group:

WWEpi Project number: PRJ2282

- LAMA or LABA only
- o LAMA+LABA
- LABA+ICS (combination product or two inhalers)
- o LABA+ICS+LAMA
- Comorbidities
 - Cardio-and cerebrovascular diseases (heart failure, myocardial infarction, stroke)
 - o Depression
 - o Anxiety
 - o Asthma
 - History of pneumonia
 - Gastro-oesophageal reflux and peptic ulcer disease
 - o Diabetes
 - Charlson score (COPD will be removed from score)
- Markers of COPD severity
 - o Previous COPD exacerbation
 - FEV1 % predicted
 - FEV1/FVC ratio
 - GOLD stage
 - MRC Dyspnoea score
- Comedications: major medication classes for each comorbidity of interest
- Smoking
- BMI
- Vaccinations
- Disability status

Further information on the definitions for the variables above will be provided in the SAP.

8.4. Data sources

The three main data sources are SLS, CPRD and SIR.

The Salford Lung Study (SLS) is described in [14]. In brief, it is a pragmatic trial, carried out in Salford, UK, to evaluate the relative effectiveness and safety of RELVAR compared with SOC. There are two separate studies within the SLS; one for COPD and the other for asthma. For this protocol, the SLS data refers to SLS for COPD only.

WWEpi Project number: PRJ2282

The CPRD is a primary care database consisting of a subset of GP practices across the UK. This will be linked to Hospital Episode Statistics (HES), socio-economic status (SES) and Office of National Statistics (ONS) datasets. For brevity, the linked dataset will henceforth be referred to as CPRD.

The SIR is a comprehensive primary and secondary care database detailing healthcare contacts, diagnostic tests and prescriptions of all patients registered with a GP in Salford, UK.

There are a range of subsets and derivations of the data sources that will be considered for this study, listed here for clarity.

CPRD: CPRD – all practices, all COPD patients

CPRD-GM: CPRD – practices/patients in Greater Manchester only, all COPD patients

CPRD-xGM: CPRD – excluding practices/patients in Greater Manchester, all COPD patients

CPRD-GM-IC: CPRD – practices/patients in Greater Manchester only, COPD patients meeting SLS inclusion criteria only

CPRD-xGM-IC: CPRD – excluding practices/patients in Greater Manchester, COPD patients meeting SLS inclusion criteria only

SLS-E: SLS – all eligible. Not all of these are enrolled (some decline)

SLS: SLS - all enrolled

SLS-SOC: SLS – SOC arm only

SIR: SIR – all COPD patients

SIR-IC: SIR - COPD patients meeting SLS inclusion criteria only

In the CPRD, data linkage will be subject to a lag due to the delayed availability of HES and ONS data. Fully linked data will only be available up to a certain date when analyses are undertaken, and as such, primary analyses will be restricted to include SLS enrolled patients up to that date. Subsequent analyses will be conducted once linkage is available for the entire recruitment period. As capture of events of serious pneumonia (as defined in the context of this study) is dependent on records of hospitalisation, PO3 will be analysed when fully linked CPRD-HES data are available.

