5. MILESTONES

Deliverable	Timelines
Contract signed	November, 2014
Agreed Protocol for GSK protocol-review forum	November, 2014†
Completion of Statistical analyses plan.	November 2014 – 1st October 2015
Development of programs for analyses.	
"Data look" SLS data and CPRD data to UoM (Interim 1).	Jan 2016
Analyses of primary objectives (PO1 only) on subset of data using "data look" data (start working on PO2/3)	Feb-March 2016
Final SLS data (one year FU for all subjects) to UoM	1 st -8 th April 2016
Analyses of PO2 (COPD exacerbation data) using final SLS data: First report with P01/P02 to GSK	By 29 th April 2016
Share output from Primary Objectives with SLS Scientific Committee; and CHESS Steering Committee	9-10 th May 2016†
First manuscript developed and ready for submission with SLS paper to Thorax based PO1 and PO2 data	June-July 2016†
Programming for secondary objectives and PO3	May-October 2016
100% CPRD-HES data available to UoM (required for PO3 analyses).	Estimated at October 2016
Analysis for PO3 and draft tables circulated	November 2016
Draft complete study report with PO1/PO2/PO3 to GSK	December 2016†
Regulatory reporting of PO3	Q1 2017
Final follow-up manuscript	Q1-2 2017†

[†] Milestone payment

WWEpi Project number: PRJ2282

RATIONALE AND BACKGROUND

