6.2. Rationale

Although the SLS will give evidence on the relative effectiveness of RELVAR compared with SOC, the SOC may be prone to the Hawthorne effect, which may distort the effect size.

The Hawthorne effect (also referred to as the observer effect) is a type of reactivity in which individuals improve or modify an aspect of their behaviour in response to their awareness of being observed. The original "Hawthorne effect" studies at the Hawthorne Works in Chicago, USA between 1924 and 1933 suggested that the novelty of being research subjects and the increased attention from such could lead to temporary increases in workers' productivity [15].

WWEpi Project number: PRJ2282

In the situation of this study, a potential Hawthorne effect may be a result of potentially different behaviours and decision making of GPs and nurses in their practices of caring for patients with COPD during the SLS study period.

Salford may not be representative of general UK population; hence the prognostic profiles, and potential effect of RELVAR in terms of the outcomes may differ in the general target COPD population compared with Salford.

Both of these issues mean that extrapolation of the results of the SLS to the wider UK population would be subject to major caveats. This proposal aims to explore, and assess how severe the caveats need to be.

RESEARCH QUESTION AND OBJECTIVE(S)

Co-primary objectives:

PO1: To characterize the patients enrolled in the Standard of Care (SOC) arm of the SLS compared with the UK population of COPD patients (using the Clinical Practice Research Datalink (CPRD)), including distribution of SES/deprivation level, to evaluate the extent to which the SLS participants are representative of the UK patient population targeted for RELVAR. The comparator set will be specified on two bases: firstly, overall, and secondly, the subset fulfilling the protocol inclusion/exclusion criteria.

PO2: To compare the rate of COPD exacerbation over the 12 months in Standard of Care arm of the SLS compared with the Standard of Care (SOC) recorded in the CPRD, in order to detect a potential Hawthorne effect or other differences.

PO3: To compare the rate of serious pneumonia (defined by hospitalisation) over the 12 months in Standard of Care arm of the SLS compared with the Standard of Care recorded in the CPRD.

Secondary objectives:

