8.3. Variables

8.3.1. Outcome definitions

Primary outcomes/endpoint:

Moderate/severe COPD exacerbations will be identified using an algorithm combining GP visits, prescriptions for oral corticosteroids and/or antibiotics, or hospital admission, as defined using information from study WEUSKOP5893. Rate of exacerbation during the 12 month follow-up will be calculated and compared with the SLS rate in the standard of care arm; if technically possible, exacerbation rates for the 12 months prior to index date (matched enrolment date) would also be compared.

• Pneumonia: To be defined as per the codelist in Table 1 (see 13.1).

Secondary outcomes/endpoints:

- Healthcare utilisation: All GP visits/encounters and all hospital admissions during the 12 month study period.
- Adherence to index prescription: Defined as percent days covered (PDC) and medication possession ratio (MPR) will also be calculated for the matched cohort, as well as discontinuation, switching medicine or adding on other medicines, to be compared with the SLS SOC arm.
- Deaths: All cause, pneumonia death, COPD-attributed death during the 12 month follow-up. For the CPRD, deaths will be determined using Office of National Statistics (ONS) linked mortality data.
- Other definitions of COPD exacerbation: Other definitions will be described as per the outputs of study WEUSKOP5893.

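### The lag rule in Protocol 8.4 is anchored on enrolment, not on 12 months of linked follow-up, so the first PO2 comparison can under-count hospital-identified exacerbations in CPRD

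*Protocol*

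**What the plan says.** Protocol section 8.4 explains that fully linked CPRD data will exist only up to some date, and therefore "primary analyses will be restricted to include SLS enrolled patients up to that date". It continues: "Subsequent analyses will be conducted once linkage is available for the entire recruitment period". Both conditions refer to entry into the study. The same section defers PO3 to full CPRD-HES linkage because serious pneumonia depends on hospital records.

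The PO2 objective is "To compare the rate of COPD exacerbation over the 12 months in Standard of Care arm of the SLS", compared with CPRD. Section 8.3.1 identifies exacerbations by "an algorithm combining GP visits, prescriptions for oral corticosteroids and/or antibiotics, or hospital admission". Section 8.1 draws CPRD index dates from the list of SLS entry dates.

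The milestone table in section 5 gives this order:

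- 1-8 April 2016: "Final SLS data (one year FU for all subjects) to UoM".
- By 29 April 2016: "Analyses of PO2 (COPD exacerbation data) using final SLS data", with the first PO1/PO2 report.
- June-July 2016: first manuscript, on PO1 and PO2.
- Estimated October 2016: "100% CPRD-HES data available to UoM (required for PO3 analyses".
- December 2016: draft complete report on PO1, PO2 and PO3.

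The code-list annex (item 2, moderate/severe exacerbation) counts hospital episodes where secondary care data exist. It also describes a primary-care-only variant for comparing CPRD with the Salford EHR.

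**The concern.** A rule meant to protect against the lag should ask whether a patient's outcome window is covered by linked data. This one asks whether the patient's entry date is. A CPRD patient indexed just before the cut-off passes, yet has almost no linked hospital follow-up. The rerun trigger repeats the slip: linkage over the recruitment period still leaves the last entrants without linked follow-up.

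The reason given for deferring PO3 applies equally to the hospital component of PO2, but PO2 is not deferred. The loss falls on one side, because the lag is a CPRD problem and SLS has one year for everyone. It lowers the CPRD rate and shifts the SLS region upward relative to the CPRD regions. Section 8.7.1 treats an SLS random effect outside the 2.5-97.5 percentile range as evidence of a Hawthorne effect, so the shift bears directly on that conclusion. It could mask a true reduction in SLS or move SLS towards the upper limit. The first report and first manuscript would carry it.

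**Working it through.** The protocol gives no figure to reproduce: no linkage cut-off, recruitment dates or share of exacerbations seen only in hospital data. Everything numerical below is an assumption shown over a range.

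**1. Dates.** From 29 April 2016 to October 2016, PO2 precedes full CPRD-HES by about five to six months.

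**2. Unlinked share of follow-up, u.** Assume uniform entry over R months, last follow-up at month R + 12, a linkage cut-off g months before that, and the same entry limit for CPRD as for SLS. Each patient's linked follow-up is min(12, cut-off minus entry).

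- For g up to 12 (cut-off at or after the end of recruitment), the enrolment rule excludes nobody. A fraction g/R of patients lack on average g/2 of 12 months, so u = (g/R) × (g/2)/12 = g²/(24R).
- For g above 12, entry runs for A = R + 12 − g months among those kept. For A of at least 12, u = (12/A) × 0.5 = 6/A.

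| R (months) | g = 6 | g = 12 | g = 18 |
|---|---|---|---|
| 18 | 36/432 = 8.3% | 144/432 = 33.3% | 6/12 = 50.0% |
| 24 | 36/576 = 6.3% | 144/576 = 25.0% | 6/18 = 33.3% |
| 36 | 36/864 = 4.2% | 144/864 = 16.7% | 6/30 = 20.0% |

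Across these cells, 4-50% of CPRD follow-up is unlinked. At g = 3 it is only 1-2%. Of the patients kept, the share with a full 12 linked months is 67-83% at g = 6, 33-67% at g = 12 and 0-60% at g = 18.

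**3. Effect on the exacerbation rate.** Let h be the share of exacerbations identified only in hospital data. If unlinked time still counts in the 12-month window, observed/true CPRD rate = 1 − u × h, and a true SLS/CPRD ratio of 1.00 appears as 1/(1 − u × h).

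- u = 0.05, h = 0.05: 1 − 0.0025 = 0.9975; ratio 1.003.
- u = 0.20, h = 0.15: 1 − 0.03 = 0.97; ratio 1.03.
- u = 0.30, h = 0.30: 1 − 0.09 = 0.91; ratio 1.10.

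At the last setting, a true SLS rate 9% below CPRD would look like no difference (0.91/0.91 = 1.00).

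**4. After the change.** Requiring index at least 12 months before the cut-off makes u = 0 by construction. The share of all enrolled patients retained is (R − g)/R:

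- R = 18: 67% at g = 6, 33% at g = 12.
- R = 24: 75% and 50%.
- R = 36: 83% and 67%.

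**The case against.** The best reply is that nothing in the protocol says unlinked months are counted as event-free. PO2 is a rate, section 8.1 already sends left truncation and survival modelling to the SAP, and censoring at linkage end would be ordinary SAP content. With such censoring there is no under-count. This stands, and the bias is therefore conditional. It does not rescue section 8.4, which states a rule of its own, on the wrong date.

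Second, the code-list annex makes hospital events conditional on available data and describes a primary-care-only variant. Used on both sides, that variant would also remove the bias. But the annex does not name it as the PO2 definition, and it would drop the hospital component that 8.3.1 includes. The documents leave open which definition governs the April 2016 report.

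Third, section 8.7.3 recognises the lag and says some analyses may need earlier data, section 8.4 foresees reruns, and a complete report is due in December 2016. A correction is possible, but it would follow the first report and planned manuscript. The stated rerun trigger is too early, and nothing marks the April result as provisional.

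Fourth, the date phrase in 8.4 might mean data up to that date. The next sentence, on the recruitment period, favours the enrolment reading.

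**Conclusion.** The stated rule is wrong for a 12-month outcome and should be changed before PO2 is run. Bias follows if the 12-month window is used as written with the 8.3.1 endpoint. It does not follow if both cohorts are censored at the linkage date or both use primary care data only. Its direction is SLS/CPRD upward. With 5-30% of follow-up unlinked and 5-30% of exacerbations seen only in hospital data, the CPRD rate is about 0.25-9% too low. The effect may be small.

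Three stronger readings are tempting but unsupported:

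- That CPRD hospital events are certainly under-counted. The protocol does not fix how unlinked time is handled.
- That the loss in total exacerbations is as large as 15%. This needs u = 0.50 with h = 0.30 (0.50 × 0.30 = 0.15), that is, only 12 months of entry before a cut-off inside recruitment. The documents establish none of these, and a cut-off after recruitment ends gives much less.
- That SO1 admissions and deaths are under-counted by 20-50%. Section 5 schedules programming of the secondary objectives for May-October 2016 alongside PO3, and the 8.4 restriction concerns primary analyses, so nothing shows that SO1 runs on truncated linkage.

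**What to change.** - **Section 8.4, restriction.** For PO2, include only SLS-SOC and CPRD patients whose index date is at least 12 months before the linkage end date. Alternatively, censor both cohorts at that date and model the rate with a person-time offset.
- **Section 8.4, rerun.** Change the trigger to linkage covering recruitment plus 12 months.
- **Section 8.3.1 and the code-list annex.** State which exacerbation definition governs the first PO2 report, identical in both cohorts.
- **Sections 5 and 11.2.** Label the April 2016 PO2 result interim, carry that label into the first manuscript, and repeat PO2 on full CPRD-HES for the December 2016 report.
- **SO1.** Apply the same follow-up rule to admissions and deaths only if they are run before full linkage.

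The cost is wording plus a rerun of a kind the protocol already foresees, and fewer patients or less person-time in the first PO2 report. Under the assumptions above, the 12-month requirement keeps 33-83% of enrolled patients for g of 6 to 12 months. If the cut-off is much earlier, it may keep few or none (none at R = 18, g = 18), and censoring with person-time is then the workable choice.

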8.5. Study size

The target sample size for the number of COPD patients enrolled in the SLS is 2,800. Study size in CPRD will be based on the prevalence of COPD diagnosis codes; this will be a minimum 2,800 to match but is expected to be considerably larger (x5-10).

WWEpi Project number: PRJ2282

8.6. Data management

8.6.1. Data handling conventions

Data handling within University of Manchester will be governed by the System Level Security Policy for the study (see Annex 1a). Quality control programming will be conducted by within GSK, following data handling SOPs.

8.6.2. Resourcing needs

Staff resources required for the project are outlined in section 2 (responsible parties).

8.6.3. Timings of Assessment during follow-up

As per SLS protocol for SLS patients. CPRD and SIR patients are observational only.

8.7. Data analysis

8.7.1. Essential analysis

All analyses will be conducted using SAS.

For PO1, distributions of the confounders and effect modifiers (as listed in Section 8.3.3) will be tabulated – summarised as proportions in each category for binary and categorical variables, and means/medians and standard deviations for continuous variables. Graphical visualisations will also be produced to aid interpretation (for example, boxplots to characterise age distributions in each population, stacked bar charts to visualise SES by population). This will be done for a series of the derived populations to separate out true differences in demographics in Salford and differences that arise as a consequence of data quality issues etc. The following comparisons will be of interest:

- CPRD-GM v CPRD-xGM: to give an indication of true demographic difference from the same data source.
- CPRD-GM-IC v CPRD-xGM-IC: as above, but restricted to patients meeting the inclusion criteria.
- SIR v CPRD-GM: to give an indication of differences arising as a consequence of selection bias of CPRD practices, and through data quality issues etc.
- SIR-IC v CPRD-GM-IC: as above, but restricted to patients meeting the inclusion criteria.
- SIR-IC v SLS-E: to give an indication of recruitment bias and physician researcher bias (at the approach stage).
- SIR-IC v SLS: to give an indication of recruitment bias (at recruitment stage).
- SLS v CPRD-xGM-IC: to indicate the difference between trial recruited, and those
 meeting the inclusion criteria outside of Salford. This is the key comparison for
 addressing PO1.

WWEpi Project number: PRJ2282

We will then move on to explicit modelling of regional variation of the characteristics within CPRD for the emboldened comparison (SLS v CPRD-xGM-IC) to ascertain whether the characteristics observed within Salford are unusual by comparison with CPRD-xGM-IC. We will take local authority regional level (anonymised) as the comparable unit to the study region for SLS. SLS will be considered unusual on a given demographic if an appropriately chosen summary statistic for that demographic (mean for continuous variables) falls outside the 2.5-97.5 percentile range.

For PO2, we will commence with exploratory analyses, similar to described above, to explore the distributions of the primary and secondary endpoints.

Hawthorne effect will be evaluated in two different ways.

Firstly, for descriptive purposes, we will measure the prevalence of the endpoints in a series of subgroups. For example, we will compare the COPD exacerbations in CPRD-xGM-IC with SLS, stratified by SES, gender, etc.

Secondly, we will take a multilevel modelling approach. For this we will combine the SLS and CPRD into one dataset (retaining an indicator of SLS membership). The hierarchies of the model will be patient -> GP practice -> local authority region (with SLS members being treated as a single distinct region) -> strategic health authority region. Strategic health authorities (population threshold of 1 million) are non-anonymised (named) regions. Local authority regions are below the population threshold so an anonymised LA marker will be available.

We will include all confounders and effect modifiers as covariates, with outcomes corresponding to the primary and secondary study outcomes (a separate model for each). Important fixed effects at the local authority level (for example, existence of community teams) will be incorporated into the model if these can be ascertained.

A final model will be selected via backward selection using AIC (Akaike Information Criterion). We will then examine the random effect of the SLS region in the context of the random effects for the other regions. Similar to the above, if the random effect of the SLS region falls outside the 2.5-97.5 percentile range, we will conclude that SOC SLS behaves unusually compared with the rest of the UK, and hence evidence of a Hawthorne effect.

PO3 will be carried out using the same approach as for PO2.

SO1 and SO2 (which pertain to comparing other endpoints, and sensitivity analyses of endpoint definition) will be carried out in the same way as PO2.

SO3 makes explicit the possible change in outcomes at commencement of SLS. We will compare outcome rates within Salford before and after the commencement of SLS, in a self-controlling case design. We will do the same thing within CPRD to control for UK-wide secular trends. This acts as sensitivity analysis to support PO2 (using controls distinct in time rather than in geography).

WWEpi Project number: PRJ2282

Additional work will take place exploring the development of methods for a framework of measuring representativeness; this is not within scope of this protocol and is described in Annex 2.1.

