8.2.2. Exclusion Criteria

Subjects meeting any of the following criteria must not be included in the restricted cohorts:

- 1. Patients with any life threatening condition or uncontrolled/clinically significant disease (code list to be specified in the Study Analysis Plan)
- Patients with unstable COPD: Patients with an exacerbation (defined by treatment with oral corticosteroids and/or antibiotic or hospital discharge listing COPD) with an onset within 2 weeks of index date. Delay index date until at least 2 weeks after the onset of an exacerbation and until the exacerbation has resolved.
- Chronic user of oral corticosteroids: Subjects who are considered to be a chronic user of oral corticosteroids for respiratory or other indications (Algorithm to be specified in the Study Analysis Plan).
- 4. In the Salford population only, those patients who are entered in the SLS and randomised to the RELVAR arm.

WWEpi Project number: PRJ2282

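### Section 8.7.1 labels SIR-IC v SLS as recruitment-stage bias, but that contrast measures selection over the approach and enrolment stages together

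*Protocol*

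**What the plan says.** Protocol section 8.4 defines three populations that matter here:

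- "SIR-IC: SIR - COPD patients meeting SLS inclusion criteria only".
- SLS-E, everyone eligible within SLS, with the remark "Not all of these are enrolled (some decline".
- "SLS: SLS - all enrolled".

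Section 8.7.1 then lists the PO1 comparisons and says what each is meant to show. Two of them concern selection into the trial: "SIR-IC v SLS-E: to give an indication of recruitment bias and physician researcher bias (at the approach stage" and "SIR-IC v SLS: to give an indication of recruitment bias (at recruitment stage". Both start from SIR-IC. No row compares SLS-E with SLS.

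The comparisons are descriptive: tabulated distributions and graphs of the variables in section 8.3.3.

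**The concern.** The two labels describe successive filters. One acts on who is approached, the other on who then enrols. The approach row names the physician-researcher component of bias and the recruitment row does not, so the second row reads as if that component had been removed. It has not, because the benchmark is still the pool from before the approach stage.

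Selective approach by physicians and refusal by patients are different threats to representativeness, and PO1 is a co-primary objective. Someone who follows the labels could report a shift produced entirely by approach as a recruitment-stage effect. Shifts in opposite directions at the two stages could be reported as no recruitment-stage effect at all.

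**Working it through.** No figure in the Protocol depends on this point, so there is nothing to reproduce. The check is an identity that follows from the definitions.

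**Inputs.** The definitions of SIR-IC, SLS-E and SLS come from section 8.4. The two row labels come from section 8.7.1. Placing SLS-E after approach and before enrolment rests on the approach-stage label of the SIR-IC v SLS-E row and on the remark in 8.4 that some of SLS-E decline.

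**Step 1: decomposition.** Let m(·) be the mean or proportion of any tabulated characteristic.

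- Approach-stage difference: A = m(SLS-E) − m(SIR-IC)
- Enrolment-stage difference: E = m(SLS) − m(SLS-E)
- Row labelled recruitment stage: m(SLS) − m(SIR-IC) = A + E

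The row departs from E by exactly A, and the two agree only if A = 0. The row above it exists to examine A, so A = 0 cannot be presumed.

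**Step 2: illustration.** The Protocol gives no proportions, so these are assumed.

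| Case | SIR-IC | SLS-E | SLS | A | E (SLS-E v SLS) | A + E (SIR-IC v SLS) |
|---|---|---|---|---|---|---|
| a | 40% | 30% | 30% | 30 − 40 = −10 | 30 − 30 = 0 | 30 − 40 = −10 |
| b | 40% | 30% | 40% | 30 − 40 = −10 | 40 − 30 = +10 | 40 − 40 = 0 |
| c | 40% | 40% | 30% | 40 − 40 = 0 | 30 − 40 = −10 | 30 − 40 = −10 |

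In case a, an approach effect appears under the recruitment label. In case b, a real enrolment effect is hidden. Only in case c, with no approach-stage difference, does the label fit.

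**Step 3: enrolled v declined.** This contrast also isolates enrolment, but on a different scale. With f the enrolled fraction of SLS-E and D those who were eligible but did not enrol:

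- m(SLS-E) = f·m(SLS) + (1 − f)·m(D)
- so m(SLS) − m(SLS-E) = (1 − f)·[m(SLS) − m(D)]

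The sign is the same, but enrolled v declined is larger by the factor 1/(1 − f). The two should not be treated as interchangeable.

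**The case against.** The best defence is that the labels are cumulative. Both rows share one benchmark, so each could be meant to show how far the population has moved from the eligible Salford pool by that stage. The text allows this reading. Against it, the second label drops the physician-researcher component although the row still contains it. Even on the cumulative reading, no listed contrast isolates who declined, and the label needs to say that it is cumulative.

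A second defence is that the three populations all appear in the list and share a benchmark, so E follows by subtracting one row from the other. Cases a and b would each show a non-zero approach row beside the disputed one. This stands. No data are lost, and the fault lies in the label and the missing direct comparison.

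A third is that the Protocol never promises to split approach from enrolment. The sentence beginning "This will be done for a series of the derived populations to separate out true differences in demographics in Salford" goes on to contrast those differences with ones arising from data quality and the like. This also stands: the aim of splitting the two stages has to be read from the row labels.

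Finally, section 8.4 does not say outright that SLS-E means patients who were approached. That reading is an inference, though a natural one from the two places given above.

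**Conclusion.** The label is wrong for what the row measures. SIR-IC v SLS is total selection over both stages, and its departure from the enrolment-stage difference equals the approach-stage difference, whatever that proves to be. The identity needs no assumed numbers. Assigning its two terms to approach and enrolment rests on SLS-E lying between those stages.

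Three stronger conclusions might be drawn, and the documents support none of them:

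- **That PO1's main answer or the Hawthorne analysis is compromised.** Section 8.7.1 says of SLS v CPRD-xGM-IC "This is the key comparison for" PO1, and only that contrast goes on to regional modelling and the 2.5–97.5 percentile rule. The PO2 and PO3 models combine SLS with CPRD and do not use SIR-IC or SLS-E.
- **That the plan would often declare a false significant recruitment bias.** No test is planned for this row, so a rejection rate would describe an analysis nobody proposes. Treating SIR-IC and SLS as independent samples would also be doubtful, since they may overlap.
- **That the point is really about which patients SIR-IC contains.** Section 8.2.2 excludes from the restricted cohorts "In the Salford population only, those patients who are entered in the SLS and randomised to the RELVAR arm". If that applies to SIR-IC, the benchmark is not the complete pool before approach, which blurs the row further. That is a separate matter, and the labelling fault would remain if the sets were aligned.

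The consequence is therefore confined to how selection is attributed, descriptively, within PO1.

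**What to change.** In section 8.7.1:

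1. Keep SIR-IC v SLS-E as the approach-stage comparison.
2. Add SLS-E v SLS as the recruitment-stage comparison. Enrolled v eligible-but-declined may be shown beside it, with a note that it has the same sign but is larger by 1/(1 − enrolled fraction).
3. Relabel SIR-IC v SLS as cumulative selection over both stages.

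The added contrast also stays within the SLS source. SIR-IC v SLS crosses sources: 8.4 limits SIR to patients registered with a Salford GP, while 8.2 extends the SLS setting to surrounding parts of Greater Manchester.

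The cost is a small wording change and one extra descriptive contrast. All the populations are already in the list, so no new data are needed.

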8. RESEARCH METHODS

8.1. Study Design

This will be an observational COPD cohort study that will utilize the CPRD and the Salford EHR system – to compare selected cohorts with SLS.

For SLS, reference/index date is study entry. This will be matched in CPRD by the following algorithm:

1. Draw up a long-list of potentially eligible individuals in CPRD (patients who would be eligible at some point during the SLS recruitment phase).

2. For each individual:

- a. Randomly sample an entry date from full list of SLS entry dates.
- b. If patient is eligible at that entry date, then they will be included, accounting for relevant immortal time biases up to that entry date, otherwise, they will be excluded. Further details on methods of reducing immortal time bias (i.e left truncated at the entry date and survival modelling) will be outlined in the SAP.

First, the COPD populations in both Salford and in the wider CPRD (excluding Greater Manchester area) will be compared. Second, we will focus on comparisons between all patients enrolled in the SLS SOC arm versus a CPRD cohort that would have been eligible for SLS as per the inclusion and exclusion criteria.

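### By the section 8.4 labels, the PO2 model (which PO3, SO1 and SO2 follow) combines both SLS arms with all CPRD COPD patients, contradicting the protocol's own SOC-versus-eligible comparison

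*Protocol*

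**What the plan says.** Section 8.4 of the Protocol sets out a list of named subsets. Three entries matter here: "SLS: SLS - all enrolled", "SLS-SOC: SLS – SOC arm only" and "CPRD: CPRD – all practices, all COPD patients". A further label, CPRD-xGM-IC, denotes CPRD patients who meet the SLS criteria and are outside Greater Manchester.

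Section 8.7.1 introduces the PO2 multilevel model with: "For this we will combine the SLS and CPRD into one dataset (retaining an indicator of SLS membership". PO3 uses the same approach, and SO1 and SO2 are to be done in the same way. The descriptive PO2 comparison just before it sets CPRD-xGM-IC against SLS. Section 8.3.2 states: "Hence the primary exposure of interest is whether a patient is enrolled in SLS (yes/no". Section 8.2.1 takes the SLS data without any restriction.

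The objectives read differently. PO2 compares the exacerbation rate "in Standard of Care arm of the SLS compared with the Standard of Care (SOC) recorded in the CPRD", and PO3 does the same for serious pneumonia. Section 8.1 announces "comparisons between all patients enrolled in the SLS SOC arm versus a CPRD cohort that would have been eligible for SLS".

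**The concern.** PO2 asks whether usual care inside the trial behaves like usual care elsewhere. That needs the SOC arm on one side and comparable, eligible patients on the other. The model is the step that answers the question, and by the protocol's own labels it is written on two wider sets. A programmer working from section 8.4 would build a different dataset from one working from the objectives.

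At stake is the meaning of the SLS region effect. The covariate list in section 8.3.3 has no term for trial arm. If RELVAR patients were in the data, any effect of RELVAR on exacerbations or pneumonia would stay in the SLS region effect. That effect is the quantity judged against the 2.5-97.5 percentile range, and a value outside the range is taken as evidence of a Hawthorne effect.

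**Working it through.** The protocol states no power, rate or effect size on this point, so there is no figure to reproduce. The check is a comparison of text, followed by an illustration on assumed inputs.

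**1. Text that points to the wide sets**
- Section 8.7.1, multilevel model: SLS and CPRD, neither with a suffix.
- Section 8.7.1, descriptive PO2 comparison: eligible controls outside Greater Manchester, but SLS again without the SOC suffix.
- Section 8.3.2: exposure is enrolment, with no arm named.
- Section 8.2.1: SLS taken as it stands.
- Section 8.2.2: RELVAR patients are removed, but only from the restricted Salford cohort. That cohort is built from the Salford Integrated Record, not from the SLS data.
- The label SLS-SOC does not occur in section 8.7.1. The PO1 list there follows the section 8.4 labels closely. Its comparison of SIR-IC with SLS is meant to show bias at recruitment, which precedes randomisation, so SLS there does mean all enrolled.

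**2. Text that points to the SOC arm and eligible controls**
- PO2 and PO3: SOC arm.
- Abstract, Population: SOC arm against CPRD patients who meet the SLS criteria.
- Section 8.1: SOC arm against an eligible CPRD cohort.
- Section 8.3.1: the exacerbation rate is compared with the SOC-arm rate.
- Section 8.9: the Hawthorne effect can be assessed for SOC only.
- Sections 8.1, 8.2 and 8.2.1: Greater Manchester is excluded from the CPRD group.
- Section 8.7.1, conclusion rule of the same model: the conclusion is drawn about SOC SLS.

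The second list is the consistent one and states the intent. The first list contains the sentence that builds the dataset.

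**3. Direction of the distortions if the labels were followed**

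Every input here is an assumption, and the true Hawthorne effect is set to none.

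*RELVAR share.* With a share s of SLS patients on RELVAR and a RELVAR:SOC rate ratio r, the apparent SLS/CPRD ratio is (1 − s) + s·r. With s = 0.5:
- r = 0.8: 0.5 + 0.40 = 0.90
- r = 0.9: 0.5 + 0.45 = 0.95
- r = 1.0: 1.00
- r = 1.1: 0.5 + 0.55 = 1.05

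*Ineligible controls.* With a share m of CPRD controls ineligible and their rate q times that of eligible patients, the crude ratio is 1/((1 − m) + m·q).
- m = 0.3, q = 0.7: 1/0.91 = 1.10
- m = 0.5, q = 0.3: 1/0.65 = 1.54

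*Both together.* With r = 0.8, m = 0.3 and q = 0.7: 0.90/0.91 = 0.99. Under these inputs the two distortions nearly cancel. Under others they do not: r = 0.8, m = 0.5 and q = 0.3 gives 0.90/0.65 = 1.38.

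The control figures are before covariate adjustment. Section 8.3.3 lists previous exacerbation and current medication group, which track the eligibility criteria, so adjustment should reduce them.

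**4. After the fix.** With SLS-SOC against CPRD-xGM-IC, s = 0 and m = 0, and both terms equal 1.

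**The case against.** The strongest reply is that the intended sets are stated repeatedly, including in the rule that closes the model's own description, so no informed analyst would pool the arms. Section 8.4 also uses CPRD as shorthand for the linked data source, so the sentence on combining can be read as merging two sources rather than naming two analysis sets. On intent this reply stands. It does not remove the contradiction: the rule draws a conclusion about SOC SLS from a dataset that no sentence in section 8.7.1 restricts to SOC.

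Four stronger readings are tempting, and the documents do not support them.
- *A reader might infer a settled plan to mix RELVAR patients and ineligible controls into the Hawthorne analysis.* The second list above rules that out.
- *A reader might infer that Greater Manchester practices will serve as controls.* The CPRD label includes them, but sections 8.1, 8.2 and 8.2.1 exclude them. Section 8.9 treats a Greater Manchester comparison as an additional one.
- *A reader might infer that the PO1 key comparison is biased because it uses all enrolled.* Randomised arms agree at baseline in expectation, so only the label and the objective's wording differ.
- *A reader might infer that section 8.5 misstates the analysed size.* It correctly gives 2,800 as the target for SLS enrolment, and its CPRD figure, "this will be a minimum 2,800 to match but is expected to be considerably larger (x5-10", carries no power claim.

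**Conclusion.** The point holds as a contradiction in the protocol about the analysis set for PO2 and PO3, and for SO1 and SO2, which follow the same model. It is not missing detail that an SAP would supply: the protocol fixes its labels and then uses them against its own objectives.

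The size of any error cannot be derived from the protocol. The illustrative shifts (0.90 to 1.05 from the RELVAR share, 1.10 to 1.54 crude from ineligible controls) rest wholly on assumed allocation, rate ratios and eligible shares. For the RELVAR rate ratios below 1 used here, the two shifts run in opposite directions. No between-region spread is given, so it cannot be shown that a shift of this order would move the SLS region across the percentile limits. The case for change rests on the ambiguity and on how easily it is removed.

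**What to change.** - **Section 8.7.1:** write SLS-SOC and CPRD-xGM-IC in the descriptive PO2 comparison and in the multilevel model for PO2 and PO3, and in the SO1 and SO2 analyses that follow it.
- **Section 8.3.2:** define the exposure on the same two sets, naming the SOC arm.
- **Section 8.2.1:** state that only the SOC arm of the SLS enters these analyses.
- **PO1 key comparison:** reconcile the label with the objective's wording. Either set is defensible at baseline.
- **Section 8.5:** no change is needed.

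The cost is wording only. No figure in the protocol changes and no further data are required.
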